6.1. Data sources

6.1.1. Context and rationale for data sources

The overall ENCORE project uses data from a total four different oncology-specific electronic health records (EHR)-derived data sources: ConcertAI, COTA, Flatiron Health, McKesson/Ontada. For ENCORE, not all databases are available for each cancer indication and the names of the databases will henceforth be blinded and referred to as ENCORE DataBase (EDB) 1, 2, 3 and 4 (the numbering does not coincide with the above order of mention of the databases).

For this trial emulation, breast cancer-specific data are available for EDB1, EDB3 and EDB4. The fitness-for-purpose of the data for the given trial emulation were assessed and considered for the final selection of the databases.

Reason for selection: All considered databases draw from a comprehensive national sample of patients with cancer in the US with detailed EHR-derived information on the information necessary to study medication effectiveness in oncology.

Strengths of data source(s): Size and detailed clinical information on oncology-specific variables and outcomes (validated composite all-cause mortality sourced from different data sources^{8,9}).

Limitations of data source(s): General limitations across all data sources include missing data, potential lack of data continuity, heterogeneous data provenance, quality/heterogeneous ascertainment of mortality endpoint data and the variability in how line of treatment is captured and curated (a more comprehensive discussion of the data sources and approaches is provided in section 7. After a comprehensive assessment of all data sources regarding their fitness for the purpose of emulating the PALOMA-2 trial, EDB4 was found insufficient to be included in the main analysis for the following reasons.

- **Rationale for excluding of EDB4 from primary analysis:** Since the study identification period (10/01/2018–09/30/2023) began after the 2015 approval of palbociclib, patients who initiated palbociclib before 10/01/2018 were only included if they survived until the start of the study period, which may introduce selection bias due to left truncation.¹⁰
- For these reasons, only EDB1 and EDB3 will be used for the main analysis. However, EDB4 will be considered as part of a sensitivity analysis to observe the results in a setting which may be impacted by selection bias (see sensitivity analysis #11 in Table 8).

Data source provenance/curation: In brief, all databases provide EHR-derived oncology-specific patient-level information which are either derived directly (e.g., through structured data fields and dropdown menu selections) from EHR and/or undergo semi-automated abstraction processes from unstructured reports. The detailed data provenance, abstraction processes and implemented business rules to curate and prioritize certain variables may vary by database and can be found in legacy publications by the data partners.

Table 3. Metadata about data sources and software.

	EDB1	EDB3	EDB4
Data Source(s):	EHR-derived	EHR-derived	EHR-derived
Study Period:	Patient identification period: 01/01/2011-04/30/2024 with follow-up information through data cut-off date on 04/30/2024	Follow-up information through June 2023 (there is no specific time period restrictions for patient eligibility)	Patient identification period: 10/01/2018-09/30/2023 with follow-up information through data cut-off date on 09/30/2023.
Eligible Cohort Entry Period:	Anytime at start of study drug initiation	Anytime at start of study drug initiation	Anytime at start of study drug initiation
Data Version (or date of last update):	Delivery: Jul 11, 2024	Delivery: Jun 16, 2023	Delivery: Oct 24, 2023 Updated (demographics): Feb 29, 2024
Data sampling/extraction criteria:	Patients are sampled if they have a confirmed diagnosis of metastatic breast cancer via abstraction on or after 1 Jan 2011, and at least 2 EHR visits on or after 1 Jan 2011. Both ICD-9 (174.x) and ICD-10 (C50.x) codes are used for the initial selection, and advanced diagnosis are then confirmed via abstraction (since ICD codes do not specify advanced diseases).	This database identifies patients for curation using a structured ICD-10 diagnosis code (ICD-10 C50*), corresponding to the indication of interest, along with at least the year of diagnosis. Once this initial screening list is generated, patients are randomly selected for further review. Curation begins with confirmation of the diagnosis and diagnosis date, primarily based on pathology reports and other unstructured data sources. All patients must be over 18 years of age at the time of their first diagnosis. Certain breast cancer cases are excluded from curation. Specifically, in-situ breast cancers such as ductal carcinoma in situ (DCIS) or lobular carcinoma in situ (LCIS) without an invasive component are not eligible. However, DCIS with microinvasion or DCIS associated with Paget's disease qualifies for curation. Additionally, in-situ breast cancers that later progress to invasive carcinoma are eligible; in	Breast cancer patients with an office visit in the reporting period will be included in the report with full patient history. Patients are sampled if they were diagnosed with breast cancer and with a documented visit date, within the defined reporting period, to one of the facilities and were at least 20 years of age at the time of first diagnosis. Patients who were on a clinical trial at any point in their treatment history are excluded.

		
these cases, the diagnosis date should reflect the date of the original in-situ diagnosis, not the later invasive diagnosis.
 
Patients are ultimately selected for inclusion in data products through quality control processes that assess consistency and potential conflicts in their records. These evaluations may rely on structured data alone or a combination of structured and curated data, depending on the specific data product. Importantly, CAI does not exclude patients based on data completeness, in order to prevent the introduction of selection bias.
	
Type(s) of data:	EHR-derived	EHR-derived	EHR-derived
Data linkage ¹ :	Mortality/date of death is a composite endpoint of structured and unstructured data from the EHR, obituary data, and the social security death index	Mortality/date of death is a composite endpoint derived from structured EHR data, manual curation, and third-party sources including obituary data and the Social Security Death Index. De-identified tokens link patients across datasets using hashed PII. Curated data is prioritized, followed by EHR and then third-party sources. Reported death dates are shifted to the nearest Sunday within four days to enhance privacy. Curated death information follows a source hierarchy: death certificate, obituary, or provider-reported date.	Mortality/date of death is a composite endpoint of structured and unstructured EHR data, supplemented with commercially available claims data, obituary data, and the Social Security Administration death master file.
Conversion to CDM ² :	No	Yes	No
Software for data management:	R 4.3.2	R 4.3.2	R 4.3.2

¹ Mortality/date of death is a composite endpoint that is often derived from various linked sources including social security death index/ Social Security Administration death master file, obituary data and EHR records

² CDM = Common Data Model

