Sensitivity #8	Using all available calendar time	This analysis explores potential confounding related to calendar time, evolving clinical practice patterns, and access to therapies.	Aims to assess the extent of confounding introduced by changes in time, treatment practices, and access to therapies.	We expect the results to be more confounded due to calendar time.
Sensitivity #9	Missingness is handled by restricting to patients with complete observations on a subset of the most important confounders (“complete cases”).	Instead of imputing data, this sensitivity analysis restricts the analysis cohort to patients with complete observations on key confounders	Data will not be imputed and missingness is assumed to be missing completely at random	The restriction to complete cases will significantly decrease sample size. To limit the attrition of patients with partially observed covariates, it won’t be possible to use all covariates used in the main analysis propensity score model, but only consider key covariates with overall low proportions of missingness (age, sex, etc.)
Sensitivity #10	Exclusion of patients with >1 year between metastasis diagnosis and index date	This sensitivity analysis varies the inclusion criteria by excluding patients whose index date (treatment start) is >1 year after their metastatic diagnosis date which is	Helps ensure that treatment reflects initial first-line treatment of metastatic disease, not late-line therapy.	Exclusion of further patients results in a smaller cohort size which may reduce statistical power.

		clinically unrealistic or implausible for a first-line treatment		
Sensitivity #11	Addition of EDB4	EDB4 is not considered in primary analyses for reasons given in section 6.1.1.	Increased sample size and potentially broader coverage of general US cancer population	See limitations listed in section 6.1.1 regarding potential immortal time and selection bias due to left truncation .
Sensitivity #12	Descriptive analysis of switching/crossover patterns in the trial and its emulation	This sensitivity analysis assesses crossover patterns comparatively in the trial and its emulation	Help to understand the potential concordance/discordance of treatment effects between the trial and its emulation	Analysis is on the description level, which may limit conclusions

7. Limitation of the methods

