Inclusion 3	Documentation of histologically or cytologically confirmed diagnosis of estrogen-receptor positive (ER+) breast cancer based on local laboratory results.	[-inf; 0]	Any ER+ or ER missing status to or on index date	Any ER+ or ER missing status to or on index date	Any ER+ or ER missing status to or on index date	If ER is missing and a patient received the exposures of interest, then ER is likely to be positive given the alignment with the indication for the exposures of interest	edbx_get_biomarker()
Inclusion 4	Previously untreated with any systemic anti-cancer therapy for their locoregionally recurrent or metastatic ER+ disease.	[MBC; -1]	No systemic anti-cancer therapy following initial record potentially indicating metastatic disease and prior to index date	No systemic anti-cancer therapy following initial record potentially indicating metastatic disease and prior to index date	No systemic anti-cancer therapy following initial record potentially indicating metastatic disease and prior to index date		
Inclusion 5	Postmenopausal women defined as women with: - Prior bilateral surgical oophorectomy, or - Medically confirmed post-menopausal status defined as spontaneous cessation of regular menses for at least 12 consecutive months or follicle-stimulating hormone (FSH) and estradiol blood levels in their respective postmenopausal ranges with no alternative pathological or physiological cause.	NA	NA	NA	NA	Although not directly captured in RWD, it is likely to be fulfilled given the alignment with the indication for the exposures of interest	
Inclusion 6	Measurable disease as defined per RECIST v.1.1 (see Appendix 7) or bone-only disease (with bone lesions confirmed by CT, MRI or bone X-ray). Tumor lesions previously irradiated or subjected to other locoregional therapy will only be deemed measurable if disease progression at the treated site after completion of therapy is clearly documented.	NA	NA	NA	NA	It is reasonable to assume that all patients in RWD had measurable disease if they received treatment	
Inclusion 7	World Health Organization Performance Status of 0 to 1	[-90; 0]	ECOG = 0 1	ECOG = 0 1	ECOG = 0 1		edbx_get_ecog()
Inclusion 7	Restriction to period 2015-2022	[0; 0]	Years 2015-2022	Years 2015-2022	Years 2015-2022		

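### Sensitivity #11 adds EDB4 with the left-truncated pre-10/01/2018 initiators still in it, so a shift in the pooled HR cannot be attributed; restrict EDB4 to index dates from 10/01/2018

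*Combined protocol and SAP*

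**What the plan says.** Section 6.1.1 gives left truncation as the only reason for leaving EDB4 out of the primary analysis: "patients who initiated palbociclib before 10/01/2018 were only included if they survived until the start of the study period". It then says that "EDB4 will be considered as part of a sensitivity analysis to observe the results in a setting which may be impacted by selection bias".

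Table 3 shows how the truncation arises. EDB4 has "Patient identification period: 10/01/2018-09/30/2023 with follow-up information through data cut-off date on 09/30/2023", and its sampling rule is "Breast cancer patients with an office visit in the reporting period will be included in the report with full patient history". Entry therefore needs a visit inside the window, and treatment history is filled in backwards. The cohort entry cell for EDB4 reads "Anytime at start of study drug initiation", as it does for EDB1 and EDB3.

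The eligibility table at the end of the appendix gives EDB4 the same index period as the other databases: "Years 2015-2022". In Table 8 (sensitivity analyses), #11 is described only as the addition of EDB4. Its rationale is "EDB4 is not considered in primary analyses for reasons given in section 6.1.1", and its limitation entry is "See limitations listed in section 6.1.1 regarding potential immortal time and selection bias due to left truncation". No index-date restriction and no delayed-entry risk set is specified. Section 6.7.1 combines the database estimates with a fixed-effects meta-analysis.

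**The concern.** The stated defect belongs to patients indexed before 10/01/2018. Those patients are eligible in #11, and OS for EDB4 is counted from the index date (section 6.6.5). Each of them carries a stretch of guaranteed survival, and their counterparts who died before sampling are absent. Section 6.1.1 mentions palbociclib initiators, but the visit-based sampling rule truncates early letrozole-alone initiators in the same way.

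If the arms have different calendar patterns, the guaranteed survival is unequal between arms and the EDB4 hazard ratio can move in either direction. The fixed-effects model then treats that ratio as an estimate of the same quantity as EDB1 and EDB3. A pooled #11 result that differs from the primary one could reflect truncation or a genuine database difference, and one that agrees could reflect offsetting errors. The strengths claimed for #11, size and coverage, are hard to realise from such an estimate.

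**Working it through.** **Plan's own figures.** Section 10.3 gives power at HR 0.92 (alpha 0.05, 50% exposed) of 0.27 for 1021 events in EDB1 and 0.11 for 331 events in EDB3. The two-sided Schoenfeld formula gives 0.265 and 0.115, so both reproduce. They are not in dispute; only the total, 1021 + 331 = 1352 events, is used below. No event count is given for EDB4.

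**Accrual before sampling.** January 2015 to 10/01/2018 is 45 months, and 2015-2022 is 96 months. 45/96 = 47%.

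**Share of early initiators who could not be sampled.** Assume exponential survival with h = ln 2 / median and uniform index dates. For a January 2015 start, P(dead before 10/01/2018) = 1 − exp(−45h). Averaged over starts from January 2015 to September 2018, it is 1 − (1 − exp(−45h)) / (45h).

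| Median OS (months) | 45h | January 2015 start | Average, pre-October 2018 |
|---|---|---|---|
| 51.2 (trial, letrozole) | 0.609 | 0.456 | 0.251 |
| 53.9 (trial, palbociclib) | 0.579 | 0.439 | 0.241 |
| 40 (assumed) | 0.780 | 0.541 | 0.306 |
| 30 (assumed) | 1.040 | 0.646 | 0.378 |

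The trial medians are from section 4. The 30 and 40 month rows are assumptions, in case real-world survival is shorter.

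**From missing patients to HR bias.** These shares are not a bias in the HR. An illustrative simulation assumed uniform index dates, control median 51.2 months, true HR 0.96, inclusion only if alive on 10/01/2018, cut-off 09/30/2023 and no confounding. For EDB4 alone it gave:

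- constant palbociclib share: unrestricted HR about 0.95-0.96, so almost no bias;
- share rising from 20% to 80%: about 1.16;
- share falling from 80% to 20%: about 0.8;
- restriction to index dates from 10/01/2018: consistent with 0.96 in every scenario, within simulation error.

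Even with constant uptake, the unrestricted control median was about 61 months, against a true 51.2. This matters because section 6.7.1 also plans a difference in median OS. Under rising uptake the unrestricted median was about 65 months, and about 51.5 after restriction.

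**Effect of the planned year covariate.** Table 5 codes index year as before 2020 versus 2020 onwards. The earlier level mixes truncated patients (2015 to September 2018) with untruncated ones (October 2018 to 2019). In the rising scenario, 1:1 matching on that binary variable moved the HR from about 1.16 to about 1.06, so roughly half the bias remained.

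**Effect on the pooled HR.** Assume 300 EDB4 events and weight by events: 300 / (1352 + 300) = 0.182. With year matching, 0.96 × exp(0.182 × ln(1.06/0.96)) = 0.98. Without it, 0.96 × exp(0.182 × ln(1.16/0.96)) = 0.99.

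**Follow-up after restriction.** Index dates 10/01/2018 to 12/31/2022 with cut-off 09/30/2023 leave 60.0 down to 9.0 months of potential follow-up. With uniform index dates, the share who could be followed to the trial's median OS is (60.0 − 51.2)/51.0 = 17% or (60.0 − 53.9)/51.0 = 12%.

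**The case against.** The plan discloses the problem twice, keeps EDB4 out of the primary analysis, and presents #11 as a look at a possibly biased setting. Estimates are produced per database before pooling, so EDB4's contribution can be seen separately, and no primary conclusion rests on #11. The size of any HR bias is unknown: the EDB4 uptake pattern is in Figure 13, which could not be seen for this review; constant uptake gives almost none; and the year covariate removes part of it. In the worked example the pooled HR moves only from 0.96 to 0.98 or 0.99. All of this stands, and it limits the weight of the point. It does not make the pooled #11 estimate interpretable, because disclosure does not separate truncation from a database difference.

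A reader might infer that a date filter removes the bias and turns EDB4 into a valid third database. The documents do not support that. The appendix says that EDB4 lacks a well-curated line-of-therapy variable and diagnoses of other malignancies. Table 3 excludes anyone ever on a clinical trial, which can happen after index. Section 6.6.5 censors at the last vital signs. Patients who started treatment elsewhere after 10/01/2018 must still survive to a qualifying visit. In simulations where 20-50% of later initiators arrived a mean of 12-24 months late (assumptions), the control median after restriction was still about 52-59 months, with little change in the HR.

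Delayed entry at 10/01/2018 itself would also be wrong. Sampling needs a documented visit, so survival is guaranteed up to that visit and not merely to the start of the window.

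**Conclusion.** The point holds as a cheap improvement to one sensitivity analysis. As specified, #11 brings back the patients who are the only stated reason for excluding EDB4, and neither restriction nor delayed entry is planned. With 45 of 96 accrual months before sampling, about 24-25% of pre-October-2018 initiators would be missing through death at the trial's median OS (31-38% at assumed medians of 30-40 months). These figures assume exponential survival and uniform index dates.

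It would be tempting to read them as the error in the HR, and they are not. The HR error depends on arm-specific calendar uptake that could not be seen here; it may be near zero or substantial, in either direction. The direction and size of the shift in the actual pooled #11 estimate cannot be derived from the documents. The primary analysis in EDB1 and EDB3 does not use EDB4 and is untouched.

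**What to change.** In #11, restrict EDB4 to index dates 10/01/2018-12/31/2022 in both arms, and pool that result with EDB1 and EDB3. Show the unrestricted version beside it if wanted, so that the difference between the two indicates how much the early initiators matter.

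If earlier initiators are kept in an adjusted analysis, use risk sets that enter at the later of the index date and the first documented visit on or after 10/01/2018, and label that analysis secondary.

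In the #11 row of Table 8, state that restriction removes only the truncation from the window start. List what remains: late entry of patients treated elsewhere, the ever-on-a-trial exclusion, line-of-therapy curation, missing other-malignancy records and vital-signs censoring.

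The cost is one date filter, a rewritten table row, and a re-run of imputation, matching and balance checks in EDB4. The price in information is fewer EDB4 patients, 9-60 months of potential follow-up (so median OS in EDB4 may be poorly determined), and a 2018-2022 calendar mix that differs from EDB1 and EDB3.

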Eligibility criteria	
 • Women aged ≥ 18 years with diagnosis of breast cancer • Histologically or cytologically confirmed adenocarcinoma of the breast • Locoregionally recurrent or metastatic disease not amenable to curative resection/radiotherapy • ER-positive status • HER2-negative status • Postmenopausal status • No prior systemic therapy for advanced/metastatic ER+ disease • Measurable disease per RECIST v1.1 or bone-only disease confirmed by imaging • WHO/ECOG performance status 0 or 1 	
 • Female aged ≥ 18 years at treatment initiation with a diagnosis of breast cancer • Diagnosis of breast adenocarcinoma via histology/pathology records • Evidence of metastatic or recurrent disease • Documentation of ER-positive (or -missing) status • Documentation of HER2-negative (or -missing) status • N/A • No systemic anti-cancer therapy* following initial record indicating metastatic disease and prior to index date • N/A • WHO/ECOG performance status of 0 or 1 within 90 days of index date 	
 • If ER is missing and a patient received the exposures of interest, then ER is likely to be positive given the alignment with the indication for the exposures of interest • If HER2 is missing and a patient received the exposures of interest, then HER2 is likely to be negative given the alignment with the indication for the exposures of interest • Although not directly captured in RWD, it is likely to be fulfilled given the alignment with the indication for the exposures of interest • It is reasonable to assume that all patients in RWD had evidence of disease if they received treatment; additionally OS primary endpoint does not require measurable disease

- No symptomatic, life-threatening visceral disease (e.g., massive effusions, >50% liver involvement)

- N/A

- No active or symptomatic CNS metastases

- Record of CNS metastases prior to or on index date

- No prior treatment with CDK4/6 inhibitors

- Exclude patients with prior CDK4/6 inhibitor exposure

- No recurrence during or within 12 months of adjuvant non-steroidal AI (anastrozole or letrozole)

- Treatment with letrozole or anastrozole ≤ 12 Months prior to date of metastatic diagnosis

- No other malignancy within 3 years

- No prior record of non-breast malignancy within 3 years

- N/A

- Restriction to the time period 2015-2022

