6.5. Study design diagram

Figure 1 depicts study design and variable measurement considerations for the emulation of the PALOMA-2 trial. The selection of key confounders/prognostic factors is driven by expert knowledge and additionally based on covariates included in the real-world prognostic score (ROPRO) which is a published and validated pan-tumor and cancer-specific prognostic score framework for overall survival.¹¹⁻¹⁵

Figure 1. Study design illustration for PALOMA-2 trial emulation.

- a. Proprietary business rules to define initiation of the line of therapy (including exposure assessment window) cannot be shared.
- b. De novo metastatic status, time initial diagnosis to T0, time from first evidence of metastatic disease to T0, smoking, family history, race/ethnicity, etc.
- c. Labs (albumin, hemoglobin, etc.) and vitals (BMI, etc.) that are part of the ROPRO prognostic score; see [Becker, Weberpals, et al. Ann Oncol 2020 \(doi: 10.1016/j.annonc.2020.07.013\)](https://doi.org/10.1016/j.annonc.2020.07.013)
- d. Intention-to-treat: death due to any reason or last observed clinical activity/sign of patient being alive or data cut-off date (whichever occurred earlier)

No observability criterion was applied because measures like continuous enrollment periods (claims data) are not available in electronic health records.

Abbreviations: MBC = metastatic breast cancer

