Sensitivity #4	Censoring date is changed to 3 months before data cut-off date	For all databases, information on mortality comes from different data sources which are updated asynchronously. To account for the potential lag of updated mortality information (ghost-time bias ³⁷), the censoring for patients without mortality event in the whole patient identification period will be moved to last sign of patients being alive/visit or 3 months before data cut-off date, whichever occurred earlier. ³⁸	Approach implements a more conservative censoring rule	Approach addresses ghost-time bias by censoring patients without a recorded death event earlier
Sensitivity #5	Delta imputation models for MNAR (tipping point analysis)	Primary multiple imputation analysis assumes MAR which	Estimates impact of deviations from MAR assumption on final	Delta parameters must be assumed and results are complex to interpret in

		may not hold for every covariate	treatment effect estimates for key covariates	multivariate missingness settings; just most important covariates or those with highest suspicion of being MNAR will be evaluated
Sensitivity #6	Re-weighting of strong risk factors and/or treatment effect modifiers distribution to match that of PALOMA-2	In the presence of effect modification, treatment effect estimates may be different if the distribution of strong risk factors/effect modifiers is different in the emulated cohort versus the trial cohort	Re-weighting adjusts for differences in distributions of key risk factors and/or treatment effect modifiers (see subgroup analysis in Table 7)	Re-weighting risk factors/potential effect modifiers to match the PALOMA-2 trial and simultaneously balancing them across treatment groups may be challenging due to differences in measurement
Sensitivity #7	Including patients who have had at least 1 visit 90 days prior to treatment initiation	EHR are often lacking data continuity, and this analysis uses the requirement of 1 visit as a proxy for continuous observation periods	Considers aspect of data continuity	There may be patients who are put on treatment immediately in which case they are falsely excluded

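### EDB1 requires two EHR visits that are not tied to index, while OS runs from index without delayed entry; women whose second visit falls after index contribute survival time guaranteed by selection.

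*Combined protocol and SAP*

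**What the plan says.** **Sampling.** For EDB1, Table 3 (Section 6.1.1) sets two conditions. The first concerns the diagnosis: "Patients are sampled if they have a confirmed diagnosis of metastatic breast cancer via abstraction on or after 1 Jan 2011". The second concerns contact with the practice, and it is worded "and at least 2 EHR visits on or after 1 Jan 2011". The visits have a calendar floor but no relation to the start of treatment.

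**Calendar windows.** EDB1: "Patient identification period: 01/01/2011-04/30/2024 with follow-up information through data cut-off date on 04/30/2024". EDB4: "Patient identification period: 10/01/2018-09/30/2023 with follow-up information through data cut-off date on 09/30/2023". Table 2 limits index dates: "Restriction to the time period 2015-2022".

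**Clock.** Table 1 (Section 5) starts follow-up on the day of treatment initiation, and Section 6.6.5 counts EDB1 OS from index. Section 6.6.4 instead starts EDB1 follow-up after the exposure assessment window ends. These statements conflict.

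**Analysis.** Section 6.7.1 plans a Cox model in the matched set and a Kaplan-Meier median difference. It mentions no entry time. The note to Figure 1 (Section 6.5) says: "No observability criterion was applied because measures like continuous enrollment periods (claims data) are not available in electronic health records".

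**Nearest planned check.** Sensitivity #7 in Table 8: "Including patients who have had at least 1 visit 90 days prior to treatment initiation". Its stated purpose is to stand in for a continuous observation period.

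**The concern.** A rule that can be satisfied after time zero selects on survival. A woman who starts treatment, makes her second recorded visit some months later and is then sampled could not have died in between. A comparable woman who did die in between is absent from the data. Counting the first woman's time from index adds event-free time with no matching risk of an event.

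If such women are more common in one arm, the OS hazard ratio is biased in that arm's favour. If they are equally common, the HR hardly moves, but both survival curves and both medians are a little too high. EDB1 carries most of the information: 1021 of 1021 + 331 = 1352 primary events, or 75.5%. The aim is concordance with a trial HR of 0.96, so even a modest systematic shift is worth removing if that is cheap.

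**Working it through.** **1. The plan's own figures.** Section 10.3 gives power at HR 0.92, alpha 0.05, 50% exposed. The Schoenfeld formula is power = Φ(√(d/4)·|ln HR| − 1.96).
- EDB1, d = 1021: √255.25 × 0.0834 = 1.332; Φ(−0.628) = 0.265 (stated 0.27).
- EDB3, d = 331: √82.75 × 0.0834 = 0.759; Φ(−1.201) = 0.115 (stated 0.11).

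Both reproduce with two-sided alpha. The matching standard error of log HR in EDB1 is 2/√1021 = 0.063.

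**2. Where the windows open.** EDB1 opens in January 2011, 48 months before the first eligible index month (January 2015). EDB4 opens in October 2018, about 45 months after it. No eligible EDB1 woman had to survive to a window opening. In EDB1 the only conditioned interval is from index to a second visit that falls after index.

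**3. How many deaths such an interval hides.** Assume exponential survival with the trial's letrozole median of 51.2 months (Section 4). P(death within g months) = 1 − exp(−ln 2 · g/51.2):

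| g (months) | deaths lost among affected women |
|---|---|
| 1 | 1.3% |
| 3 | 4.0% |
| 6 | 7.8% |
| 12 | 15.0% |

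**4. Effect on the HR, closed form.** Let a fraction f of an arm have the second visit g months after index, with follow-up to C = 60 months. Write S = exp(−λg) and K = exp(−λC). Among women sampled:
- events = (1−f)(1−K) + f(S−K)
- time counted from index = (1−f)(1−K)/λ + f[Sg + (S−K)/λ]

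The apparent rate is events divided by time. Take λ = ln 2/51.2 = 0.01354 for letrozole and 0.96λ for palbociclib plus letrozole.

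Largest case, f = 20% letrozole and 5% palbociclib, g = 12:
- letrozole 0.5262/40.91 = 0.01286
- palbociclib 0.5343/41.62 = 0.01284
- ratio 0.998

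The shift is ln(0.998/0.96) = 0.039, or 0.62 of the EDB1 standard error. Other cases:

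| letrozole f | palbociclib f | g | apparent HR (true 0.96) |
|---|---|---|---|
| 10% | 5% | 6 | 0.967 |
| 10% | 5% | 12 | 0.972 |
| 20% | 5% | 6 | 0.980 |
| 5% | 10% | 6 | 0.954 |
| 5% | 10% | 12 | 0.948 |
| 20% | 20% | 6 | 0.960 |
| 20% | 0% | 1 | 0.965 |

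**5. Simulation check.** There were 1.5 million women per arm, control median 45 months, true HR 0.96, delays uniform from zero to twice the mean, and assumed censoring uniform over 16 to 112 months. Women who died or were censored before the qualifying visit were removed. For the arm-imbalanced cases with mean delays of 6 or 12 months, the Cox HR from index ran from about 0.946 to 0.997, in line with the table. Delayed entry returned 0.957 to 0.962 throughout, which is 0.96 within simulation error. With 10% affected in both arms, each median rose by about 0.5 months (mean delay 6) or 1.0 to 1.1 months (mean delay 12), and most of that cancels in the planned median difference.

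**The case against.** **No evidence that it happens.** No passage gives the share of women with a late second visit, the gap, or any difference by arm. Many women will have been seen at least twice before first-line treatment starts, and for them nothing is truncated. This stands, and it is why the size can only be shown as a range.

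**Small against the precision.** Even 20% against 5% with a 12-month delay moves the estimate by less than one EDB1 standard error. This also stands. It makes the point a cheap improvement and no threat to the study, although bias, unlike the standard error, does not shrink with more data.

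**Sensitivity #7 covers it.** In part. Requiring a visit in the 90 days before treatment removes women first seen after index. It asks for one visit and the sampling rule asks for two, so a woman seen once before index and again only later remains. It also drops women where the time at risk could be corrected.

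**The EDB4 parallel.** A reader might infer that this is the same left truncation that took EDB4 out of the primary analysis, and that the plan applies a double standard. The documents do not support that. EDB4 was removed because earlier initiators "were only included if they survived until the start of the study period, which may introduce selection bias due to left truncation", a calendar date up to about 45 months after index. EDB1's window precedes every eligible index date.

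**The Figure 1 note.** It does not claim that an observability rule is impossible. It says none was applied because enrolment-type measures are missing. The fair comment is that visit dates exist and Sensitivity #7 already uses them.

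**Conclusion.** The point holds in a limited form. In EDB1, time from index to a second visit after index is conditioned on survival, the plan counts it as time at risk, and no planned analysis fully addresses it. HR bias requires an imbalance between arms. Under assumed shares of 5-20% and mean delays of 6-12 months, 0.96 becomes roughly 0.95 to 1.00. It is negligible with equal shares or delays of about one month. Absolute medians are slightly inflated either way. These sizes rest on assumed shares and gaps, exponential survival and proportional hazards.

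Two wider readings are not supported. Time before the second visit is not immortal for EDB1 women in general, only for those whose second visit follows index. The problem also does not extend to EDB3: Table 3 gives no visit-count rule there, and entering women at their first Table 4 activity would change nothing, because Table 4 includes therapy start dates and index is itself one.

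**What to change.** 1. Reconcile Table 1 and Section 6.6.5 with Section 6.6.4 on when EDB1 follow-up starts.
2. In Section 6.7.1, for EDB1 only, let each woman enter the risk set at the later of that start and her second EHR visit on or after 1 January 2011, in both the Cox and Kaplan-Meier analyses. Women with both visits by then are unchanged.
3. Report by arm the number of women whose second visit falls after the start of follow-up, and the distribution of the gap.
4. Amend the Figure 1 note to say that visit dates are used in this way.
5. Make no change in EDB3.

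**Cost.** One derived date and a start-stop survival object; visit dates are already needed for Sensitivity #7. Slightly fewer women are at risk early. A few will contribute no time: those whose second visit is their last record, since Section 6.6.5 censors at the last visit or treatment encounter, and those whose death date, imputed to mid-month or mid-year, precedes the second visit. They should be counted and reported. Section 6.7.1 already excludes women whose imputed death date gives negative follow-up, so there is a precedent. Delayed entry also assumes that, once entered, late-entering women have the same hazard as those already at risk in their arm; the counts in step 3 will show whether that matters.
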